***Correcting Residual Errors With Spectral, Ultrasound, Traditional Speech Therapy
(C-RESULTS-RCT)***

Protocol NCT03737318

Updated 12/8/2025

MASTER PROTOCOL FOR C-RESULTS RCT

Goal of study: Compare response to two types of visual biofeedback (ultrasound and visual-acoustic) versus traditional motor-based treatment for residual speech errors.

Primary outcome measure: Acoustically measured accuracy of within-session trials from Phase I (Acquisition).

Secondary outcome measure: Perceptually rated accuracy after Phase II (Generalization).

Functional outcome measure: Socioemotional questionnaire before vs after treatment.

Hypothesis: Mixed-effects models investigating the primary outcome measure will show a significant advantage for biofeedback over traditional motor-based treatment as early as the first day of Phase 1, and no later than the final day.

Enrollment: Target 55 kids in each of 2 sites (MSU, Syracuse), total n = 110

0. Pre-screening

- Phone screening to ask about all major exclusionary categories
 - Use Phone Screening Script
 - Additionally, review Parent Questionnaire for any responses that do not meet exclusionary criteria specified in Phone Screening Script.

1. Evaluation Session 1:

- Goal: Determine eligibility for inclusion in study; collect baseline measures for use in predicting response to treatment.
- See "Checklist for C-RESULTS Evaluation - Day 1"
 - Consent and assent; parent history form, demographic and socio-emotional questionnaires
 - Must be between 9;0 and 15;11 at time of enrollment.
 - Must have been exposed to English no later than age 3.
 - English must have equal or dominant status. Balanced bilinguals are okay.
 - Must speak a rhotic dialect of English; presence of one or more non-rhotic speakers in the home is exclusionary.
 - ADHD is admissible; other neurobehavioral disorders (ASD, OCD, Tourette's) are exclusionary.
 - History of CAS / learning disability / dyslexia is admissible if participant meets cutoff scores on eval day 1. Other developmental disorders are exclusionary.
 - History of permanent hearing loss is exclusionary. Temporary hearing loss due to otitis media, including recurrent OM/tubes, is admissible.
 - Hearing screening in soundbooth at 20 dB HL (500 Hz, 1000 Hz, 2000 Hz, and 4000 Hz)—must identify 2/3 tones at 20 dB at each frequency for inclusion.

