 - Probes for /r/: Sentence, Word, Stimulability
 - Rake-wake discrimination task
 - Bite block task
 - Category goodness task
 - Phonetic awareness task

4. Treatment targets

- Target variants:
 - syllabic /ɛ/, vocalic front vowel context, vocalic back vowel context, consonantal front vowel context, consonantal back vowel context.
- All participants will practice all variants in all phases of treatment.

5. Phase 0: Dynamic assessment

- Dynamic Assessment will consist of a single 90-minute session of traditional motor-based (non-biofeedback) instruction. The goal is to evaluate participants’ stimulability in detail and classify them into stimulability categories for randomization.

MASTER PROTOCOL FOR C-RESULTS RCT

- Same protocol as Phase I: Acquisition (see below), including both pre-practice and structured practice, but with no biofeedback.
 - Instruction (~25 min): Discuss tongue shapes for /r/. Use “Script_Introducing tongue shapes for r_Dynamic_Assessment_CRESULTS,” plus Tiede et al poster, followed by 2-minute break.
 - Pre-practice (until performance criterion met or session-level timer reaches 44 minutes): Relatively unstructured practice guided by the Prepractice Tally Sheet, with model and KP on every trial, followed by a 2-minute break.
 - Structured syllable practice (44 min).
- Based on the treating clinicians’ perceptual ratings of participants’ performance in Phase 0, participants will be categorized as high responders (>5% accuracy during Dynamic Assessment) or low responders (0-5% accuracy).

6. Randomization

- Overview:
 - Randomization will be supervised by the study statistician at the central site (NYU).
 - Randomization will be stratified by site and severity.
 - Randomization will be proportioned in a 3:3:4 ratio (ultrasound biofeedback : visual-acoustic biofeedback : traditional motor-based treatment) at each site.
- Approach:
 - The study statistician will generate confidential participant treatment assignments in batches of 10, where each batch of 10 corresponds to a combination of site (Montclair State University versus Syracuse University) and response category (high versus low).
 - Random assignments will be generated to ensure the following distribution per batch: 3 individuals assigned to receive visual-acoustic biofeedback, 3 to receive ultrasound biofeedback, and 4 to receive MBT.

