 - The first 4 batches will correspond to the first 10 participants recruited in each of these site-by-category combinations. The second 4 batches will correspond to the same site-by-category combinations for the next time period.
 - The PIs will monitor allocation of participants to response categories within each site to understand whether the distribution is reasonably balanced. If it is, the final 4 batches will be assigned similarly. If not, the treatment assignment may be altered.

7. Phase 1: Acquisition

- Overview:
 - Goal: Measure response to a brief but intensive period of treatment (3 sessions, each 1.5 hours long, in 1 week).
 - Use document “Checklist for CRESULTS Intensive Treatment—Traditional,” “Checklist for CRESULTS Intensive Treatment—Ultrasound,” or “Checklist for CRESULTS Intensive Treatment—VA”
- Pre-practice (max 44 min; could be less if participant meets performance criterion to advance to structured practice):
 - In first session only, provide condition-specific instructions (approximately 25 minutes):
 - Using “Script_Introducing ultrasound_CRESULTS” document, “Script_Introducing VA_CRESULTS,” or “Script_Introducing traditional treatment_CRESULTS.” After first session, pre-practice should be broken into two 20-min blocks of practice separated by one obligatory 2-minute break.
 - Pre-practice should involve relatively unstructured, highly interactive elicitation; provide models and placement cues using document “Articulator placement cues_CRESULTS.”

MASTER PROTOCOL FOR C-RESULTS RCT

- Keep track of participant's correct productions using document "Pre-Practice Tally Sheet." Pre-practice will start by eliciting /ʒ/. A model and KP feedback should be provided on every trial. Once a particular target has been produced three times in a fully correct fashion (use a strict standard) in pre-practice, move on to another target. (Can shape from the previous target.)
 - If participant produces at least five syllable targets three times in a fully correct fashion (=15 total), move on to Structured Practice.
- If participant is assigned to a biofeedback condition, visual biofeedback remains available throughout pre-practice.
- Take a 2 minute break (obligatory) between pre-practice and structured practice.
- Structured practice (44 min; could be more or less depending on performance and time spent in pre-practice):
 - Number of trials

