- Goal: Evaluate change in time since treatment; administer perturbation tasks (NYU/MSU only) and accompanying perception tasks (all sites).
- See 1-Checklist for CRESULTS_Evaluation_PostTx2_RCT_ALLTasks (NYU/MSU) or 1-Checklist for CRESULTS_Evaluation_PostTx2_RCT_NoPerturbation (Syracuse) in CRESULTS Planning Folder/4c - Evaluation_COVID_CRESULTS/Post-Tx Evaluation 2 - RCT
- Probes for /r/ (if a child is being evaluated more than 6 weeks post treatment, don't administer probes; use 1-Checklist for CRESULTS_Evaluation_PostTx2_RCT_NoProbes)
- Head-had identification task
- Head-had discrimination task
- Reflexive perturbation task (NYU/MSU only)
- Adaptive perturbation task (NYU/MSU only)

12. Analysis Plan

- All analyses will be conducted following the intent-to-treat principle. For participants who drop out, missing data will be multiply imputed based on information collected about them prior to their loss to follow-up.
- For our primary outcome (Acquisition), we will fit a multilevel model with measures nested within study participants and words. The dependent variable will be F3-F2 distance in /r/ targets produced in each day of Phase 1 treatment. The primary independent variable of interest is group (traditional motor-based treatment versus biofeedback, with visual-acoustic and ultrasound biofeedback types pooled for this analysis). The model will also adjust for site, performance response category based on Dynamic Assessment (high responder versus low responder), acquisition day (1, 2, or 3, treated as categorical), and pre-treatment accuracy (mean F3-F2 distance across /r/ sounds in the word probe elicited in the first pre-treatment evaluation). If a within-session time trend is supported by the data, we will extend the model to account for time trends across trials within each day of treatment. Random intercepts will be included to reflect the fact

MASTER PROTOCOL FOR C-RESULTS RCT

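### Does the clause allowing assignment to change for the final batches threaten the 3:3:4 allocation?

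*Combined protocol and SAP*

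**What the plan says.** All of this is in the combined protocol and SAP, mainly section 6 (Randomization).

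- **Ratio by site:** "Randomization will be proportioned in a 3:3:4 ratio (ultrasound biofeedback : visual-acoustic biofeedback : traditional motor-based treatment) at each site".
- **Ratio by batch:** "Random assignments will be generated to ensure the following distribution per batch: 3 individuals assigned to receive visual-acoustic biofeedback", with 3 to ultrasound and 4 to MBT making up the ten.
- **What a batch is:** "each batch of 10 corresponds to a combination of site (Montclair State University versus Syracuse University) and response category (high versus low").
- **Sequence:** four batches, one per cell; four more in the same cells; then a last four.
- **Monitoring:** "The PIs will monitor allocation of participants to response categories within each site to understand whether the distribution is reasonably balanced".
- **Consequence:** "If it is, the final 4 batches will be assigned similarly. If not, the treatment assignment may be altered".
- **Oversight:** "Randomization will be supervised by the study statistician at the central site (NYU"). The same statistician generates the confidential assignments.

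The enrolment line at the front of the protocol reads: "Enrollment: Target 55 kids in each of 2 sites (MSU, Syracuse), total n = 110". Section 12 (Analysis Plan) says of the primary model: "The model will also adjust for site, performance response category based on Dynamic Assessment (high responder versus low responder), acquisition day", followed by pre-treatment accuracy. Enrolment period is not among the covariates.

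**The concern.** The clause is triggered by a baseline count with no stated threshold, and what it permits is undefined. Read literally, it could cover a change in the arm ratio for the last batches.

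Such a change would cure nothing, because stratified batches already keep the arms in proportion inside each cell. It could also do harm. Children enrolled late would be over-represented in one arm, and the primary model has no term for period, so any drift over time in case mix or delivery would leak into the comparison of biofeedback with MBT.

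The trigger is also likely to be met. Each cell has three planned batches, and the text gives no rule for a cell that fills before its site reaches 55.

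**Working it through.** **1. The plan's own ratio.** 3 + 3 + 4 = 10 per batch. For 110 children this gives 110 × 0.3 = 33, 33, and 110 × 0.4 = 44. The stated ratio reproduces. Twelve batches give 12 × 10 = 120 places for 110 children. A list longer than the target is not an inconsistency.

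**2. Does an uneven high/low mix disturb the ratio?** With h high and 6 − h low batches at a site, the arms are (3h, 3h, 4h) among high responders and (3(6 − h), 3(6 − h), 4(6 − h)) among low responders. Every h from 0 to 6 gives 18:18:24 at the site. With 55 children per site and a last batch cut short (20,000 simulated trials per split, from 5/50 to 50/5), MBT averages 22.0 per site, with a range of 19 to 24. No cell is more than 2 children away from its 40% MBT share. An uneven mix therefore gives no reason to alter the ratio.

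**3. How often will a cell overflow?** Three batches give 30 places per cell, so 55 children fit only if the split lies between 25/30 and 30/25. Let X be the number of high responders at a site, X ~ Bin(55, p). The true share p is not in the documents, so a range is shown.

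| p | P(25 ≤ X ≤ 30), one site | Both sites | Expected children beyond 30 in the larger cell, per site |
|---|---|---|---|
| 0.5 | 0.581 | 0.338 | 1.09 |
| 0.6 | 0.234 | 0.055 | 3.44 |
| 0.7 | 0.011 | 0.0001 | 8.51 |

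The value at p = 0.5 is the maximum over all p. The last batches will therefore often need to be redirected. Occasionally an extra one is needed: a 33/22 split takes 4 + 3 = 7 batches, against six planned per site.

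**4. What does redirecting at 3:3:4 cost?** In simulation (40,000 trials, p from 0.5 to 0.8, further batches issued in whichever cell fills, last batches incomplete), some arm is off 33:33:44 by more than 2 in about 10% of trials and by more than 3 in about 1%. MBT lies between 41 and 47 in about 99%. For a simple two-group comparison in SD units:

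- planned: sqrt(1/66 + 1/44) = 0.1946
- MBT at 41: sqrt(1/69 + 1/41) = 0.1972, a rise of 1.3%

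**5. What would a ratio change do, if one were made?** All inputs here are assumptions, since the documents give none: 80 children at 3:3:4 (32 MBT, 48 biofeedback), the last 30 at another ratio, and a step drift between periods. Bias = drift × difference between arms in the share enrolled late.

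- Last 30 at 15:15: 15/47 − 15/63 = 0.319 − 0.238 = 0.081. Bias is 0.016 SD at a drift of 0.2 SD (8% of the standard error) and 0.041 SD at 0.5 SD (21%).
- Last 30 at 6 MBT to 24 biofeedback: 24/72 − 6/38 = 0.333 − 0.158 = 0.175. Bias is 0.035 SD (18%) and 0.088 SD (45%).

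Only a marked ratio change combined with a large drift would matter, and the documents point to neither.

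**The case for a change.** The strongest case for a change is that the clause speaks of altering treatment assignment, not of redirecting batches, so a literal reader could change the ratio. That would create an imbalance that was not there before. Assume, for illustration, 10 high and 2 low batches, with the last four high batches switched to 2 MBT and 8 biofeedback. High responders then make up 32/40 = 80.0% of MBT and 68/80 = 85.0% of biofeedback, against 83.3% in both at 3:3:4. Adjusting for response category deals with that imbalance but not with enrolment period. The trigger is likely to be met, nobody is named to decide, and one sentence of wording would close the gap.

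Part of this stands. The wording is loose, a ratio change is not expressly excluded, and the final decision-maker is not stated.

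Three things limit it:

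- A ratio change would contradict two statements in the same section, one fixing 3:3:4 by site and one by batch. The sentences around the clause are about which cell each batch serves. Assigning the last four similarly means one per cell, and the alternative is to send them elsewhere.
- The trigger is a category set in the Dynamic Assessment, before randomization. It uses neither outcomes nor arm totals, so it cannot steer the result.
- The overflow probabilities measure how often a cell fills, not how much bias follows. They are a reason for the flexibility, not evidence against it.

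**Conclusion.** The concern does not call for a change. The clause leaves out detail that the study statistician, who supervises randomization and generates the lists, would supply sensibly: keep every batch at 3:3:4, point the last ones to the cells that are filling, and issue another if a cell runs out. Followed that way, the plan gives a sound comparison. Arms stay within a few children of 33:33:44, and the loss of precision is about 1.3% at the edge of the likely range.

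This rests on reading the clause together with the fixed ratios in the same section. The contrary reading needs a ratio change that the documents nowhere state, and its bias cannot be sized from them. Under the assumptions shown, it runs from 8% to 45% of a standard error, with the upper end requiring both an extreme ratio and a drift of 0.5 SD. Writing the natural reading down would do no harm, but it would not alter the design, the analysis or the result.

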8. Midterm administration of safety check

- At the start of Generalization Session 7: Follow Protocol for Safety Check
- Collect participant responses to the following questions:
 - “Since the beginning of this study, have you experienced any possible side-effects?”
 - “Is there anything you would like us to know about how the study may have affected you, positively or negatively?”

9. Phase II: Generalization

- **At the start of the generalization sessions 1 and 9:** Re-administer Stimulability Probe, CPP word- and sentence-level /r/ probes.
- All participants will receive two treatment sessions per week for 8 weeks (16 sessions). Sessions will be a maximum of 60 minutes in duration.
- Use CPP and Checklist for Tx Generalization CRESULTS
- Each session begins with pre-practice (maximum 10 minutes).
 - Pre-practice should include two stimulus items from each of the 5 target variants and focus on the level of complexity the child left off at in the previous session, plus or minus one level.
 - Use CPP examiner view to identify two target items per variant (10 total) that will be targeted in pre-practice; write them in the pre-practice tally sheet.
 - Terminate pre-practice once child has produced all 10 items three times in a fully correct fashion, or 10 minutes has elapsed (whichever comes first).
- Structured practice:
 - Number of trials
 - Maximum 250 /r/ trials. Target minimum 200 trials, but if cumulative session duration reaches 1 hour, terminate session.
 - After 100 trials, CPP will prompt user to take a 2-minute break. CPP should not resume function until 2 minutes have elapsed. If CPP prompts a break with 5 minutes or less remaining in the session, OK to override the break (press s).
 - Targets
 - Syllables/words targeted in each session will be randomly selected by the CPP program from standard lists of words/syllables. A separate set of syllables/words should be selected at the start of each session.
 - Words will be elicited via the CPP program in blocks of 10 trials.
 - At the base level, sessions should feature 10 items total, with 2 syllables/words representing each variant. However, if the participant moves up a level (see *Across-session manipulations*), a new set of words will be drawn, resulting in >10 words occurring in the session.
 - Within-session manipulations: The following changes may take place within a treatment session.

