 - At the carrier phrase level and above, words will be randomly selected from any of the preceding levels (**excluding** the syllable level) and presented in the appropriate context by the CPP.
- In blocked practice, each block begins with a direct model for the client to imitate.
 - Fade models once random practice is initiated.
 - If client makes a reading error, try to cue the target without modeling—start with a semantic cue, then a rhyme cue.
- Across-session manipulations: If the participant's accuracy across all trials in the previous session was equal to or greater than 80%, the CPF program will adjust the order of presentation.
 - 3 levels: Fully blocked (each target word presented in two consecutive blocks [2 words per variant; program randomly rotates through all variants]); random blocked (each block elicits 10 trials of a single word, but across blocks, different words and variants can be presented in random order [4 words per variant]); fully random (different words and variants represented within each block).
- The CPP will provide reinforcing messages at the end of each block.
 - If the participant has achieved a new milestone (e.g., advancing to a new level; first time getting 6/10 correct in a block), the CPP will report this.
 - If there is no new milestone, CPP should report number of trials completed.

MASTER PROTOCOL FOR C-RESULTS RCT

- Milestone/number of trials message should be paired with a message to encourage continued effort (Growth Mindset).

10. Post-test I (immediately after treatment)

- Goal: Evaluate progress; re-administer a subset of sensory measures elicited initially.
- See "Checklist for C-RESULTS_Evaluation_PostTX_RCT"
- Probes for /r/ and other sounds: Stimulability Probe for C-RESULTS, CPP word- and sentence-level /r/ probes, CPP tongue complexity probe
- Rake-wake identification task
- Rake-wake discrimination task
- Goodness judgment task
- Phonetic awareness task
- **Final administration of safety check**
 - Follow Safety Monitoring Protocol
 - Collect participant responses to the following questions:
 - "Since the beginning of this study, have you experienced any possible side-effects?"
 - "Is there anything you would like us to know about how the study may have affected you, positively or negatively?"
 - Also collect Post-Treatment Social-Emotional Impact and Therapy Experience questionnaires

11. Post-test II (6 weeks after treatment)

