- Finally, we will analyze survey data using a similar model, with impact score as the outcome variable and fixed effects of time, treatment group, and the time-treatment interaction, as well as site, performance response category based on Dynamic Assessment, and pre-treatment accuracy. We will again estimate the interaction between time and treatment group to evaluate whether the functional impact of treatment differs across biofeedback versus MBT conditions.

13. Fidelity Checking Plan

- Treatment sites perform fidelity checks on each other to avoid breaking blinding for data site.
- Fidelity checks should be conducted on an ongoing basis.
- Randomly select a subset of sessions from each session type:
 - For DA, complete fidelity checks on 20% of subjects per site.
 - For Acquisition, randomly select one of the three sessions per subject per site.
 - For Generalization, randomly select one from the first half and one from the second half of treatment per subject per site.
- Re-score a subset of trials to check agreement across sites.
 - Re-score tone trials only in acquisition sessions slated for fidelity checking.

Data analysis plan

All analyses will be conducted following the intent-to-treat principle, comparing participants based on the treatment assigned regardless of subsequent exposure. To maintain the full sample, missing data will be multiply imputed for participants who drop out of the study using the *mice* package [45] in the R statistical software language [46]. This approach will capitalize on information collected on these participants prior to their loss to follow-up.

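### The protocol schedules its side-effect questions only at Generalization Session 7 and Post-test I, with no check at withdrawal, so a child who leaves the study before Session 7 has no scheduled response

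*Combined protocol and SAP*

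**What the plan says.** Section 8 (the midterm safety check) gives the first occasion: "At the start of Generalization Session 7: Follow Protocol for Safety Check". The child is asked two things: "Since the beginning of this study, have you experienced any possible side-effects", and whether the study has affected them for better or worse. Section 10 (Post-test I) repeats both questions under the label "Final administration of safety check" and adds the instruction "Follow Safety Monitoring Protocol".

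No safety question is listed for the evaluation sessions, Phase 0, Acquisition, Generalization Sessions 1 to 6 or Post-test II. The document describes no withdrawal visit, no contact after early stopping and no session-by-session recording of side effects.

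The plan does expect dropout. The Data analysis plan states that "missing data will be multiply imputed for participants who drop out of the study", and section 12 says the same. Neither describes any analysis of the side-effect responses.

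Section 9 already has an assessment point soon after Acquisition: "At the start of the generalization sessions 1 and 9: Re-administer Stimulability Probe, CPP word- and sentence-level /r/ probes".

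**The concern.** Both occasions are visits that the child must attend. A child lost to the study before Session 7 reaches neither, so by default the side-effect record describes children who got at least as far as Session 7. If leaving early is related to how treatment was tolerated, that record is a selected one, and a low count of side effects cannot be taken at face value. The trial enrols children aged 9 to 15, and the document names no other source of side-effect data. Dropouts' outcome data have a stated missing-data rule; their safety responses have none, and the plan does not ask for a count of children without a response.

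**Working it through.** **Position of Session 7 in the course.** The inputs are the section 7 Acquisition schedule (3 sessions of 1.5 hours in one week) and the section 9 Generalization schedule (two sessions a week for eight weeks, each at most 60 minutes).

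- Generalization sessions: 2 × 8 = 16, which reproduces the protocol's figure.
- Post-randomisation sessions in total: 3 + 16 = 19.
- Post-randomisation sessions before the first question: 3 + 6 = 9, and 9/19 = 47%.
- Maximum minutes before the first question: 3 × 90 + 6 × 60 = 270 + 360 = 630.
- Maximum minutes in total: 3 × 90 + 16 × 60 = 270 + 960 = 1,230, and 630/1,230 = 51%.
- Weeks, if Generalization follows Acquisition directly: 1 + 6/2 = 4 of 1 + 8 = 9.

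Phase 0 is left out because it precedes randomisation and uses no biofeedback for anyone. Including its single 90-minute session gives 10 of 20 sessions and 720 of 1,320 minutes (55%). On either count, about half of treatment precedes the first question.

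**Children without a scheduled response.** The target is 110 children, allocated 3:3:4, so 60% are assigned to biofeedback and 40% to motor-based treatment. The documents give no dropout rate. The fraction d leaving the study before Session 7 is therefore an assumption, and the number without a response is 110 × d:

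- d = 2%: 2.2 children
- d = 5%: 5.5
- d = 10%: 11.0 (6.6 biofeedback and 4.4 motor-based, if dropout is equal by arm)
- d = 20%: 22.0

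**What selection could do (illustration only).** Suppose 5% of the children who are asked report a side effect, and d = 10%. If a proportion r of early leavers had one, the rate over all children is 0.90 × 0.05 + 0.10 × r:

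- r = 5%: 0.045 + 0.005 = 5.0%, so there is no distortion.
- r = 25%: 0.045 + 0.025 = 7.0%.
- r = 50%: 0.045 + 0.050 = 9.5%.

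The observed figure is 5% in all three cases. The 5%, d and r are assumed; nothing in the documents says which case is closest.

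**The case against.** The strongest reply is that both checks defer to procedures outside this document: section 8 to a safety-check protocol, section 10 to a safety monitoring protocol. Neither was supplied. Either one, or the session checklists, may provide for early stopping or volunteered complaints. This stands, and it limits the point to what this protocol schedules.

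Four stronger readings are tempting, and the documents do not support them.

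- A reader might infer that every child who stops treatment early is never asked. Besides the unseen safety documents, stopping treatment is not the same as leaving the study. Analysis is by assigned treatment whatever exposure follows, and nothing makes Post-test I conditional on completing the sessions. A child who stops treatment but attends Post-test I is asked about the whole study.
- A reader might infer that the record covers only children who stayed to the end. A child who leaves between Session 7 and Post-test I has already answered for everything up to Session 7. Only the later sessions go unasked.
- A reader might infer that the arms contrast most in Acquisition, so that the loss must bias the arm comparison. This is not shown. Biofeedback in Generalization starts at the same 80% of trials and is faded only as the child advances. Generalization also allows up to 16 × 250 = 4,000 trials, against 3 × 200 = 600 in Acquisition.
- A reader might attach a confidence bound to a report of zero side effects in an arm and then call it invalid. The plan contains no such analysis, and safety is not a listed outcome.

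It can also be said that the question looks back to the start of the study, so retained children do report on Acquisition, with about three weeks' recall. Nothing shows that this recall is inadequate. For those children the extra check is an improvement and does not correct an error. Its main value is for children who reach Generalization Session 1 but leave before Session 7.

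**Conclusion.** The point holds as a gap in this protocol's safety schedule. The two questions are set for two attended visits and for no withdrawal contact, so a child who leaves the study before Session 7, after up to 9 of 19 post-randomisation sessions, has no scheduled side-effect response here. The number affected is unknown: about 2 to 22 of 110 if 2% to 20% leave that early, which is an assumed range. Whether the record would be distorted depends on whether early leavers differ in side effects from children who are asked, and the documents do not say. The conclusion also depends on the separate safety protocol not already covering early leavers. Only safety reporting is at stake.

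**What to change.** In section 8, add two occasions for the same two questions:

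1. The start of Generalization Session 1, where probes are already re-administered.
2. At, or by phone soon after, any withdrawal, with the reason recorded. If the safety protocol already requires this contact, a cross-reference to it is enough.

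In the analysis plan, state that side-effect responses will be reported by assigned arm over all randomised children, with the number per arm who have no response. If enrolment is already complete, this count can still be reported.

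The cost is small: protocol and checklist wording, two questions at an existing visit, and one short call per withdrawal. Some withdrawn families will not be reached; they should be counted as having no response.

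### No side-effect question is scheduled at Post-test II, so the weeks after treatment and that visit's new procedures fall outside solicited safety follow-up

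*Combined protocol and SAP*

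**What the plan says.** Section 8 places the first safety check part-way through Phase II: "At the start of Generalization Session 7: Follow Protocol for Safety Check". Section 10 places the second at Post-test I, immediately after treatment, under the label "Final administration of safety check", with the instruction "Follow Safety Monitoring Protocol". Both checks use the same two questions. One is "Since the beginning of this study, have you experienced any possible side-effects"; the other is an open question about how taking part may have affected the child, for better or worse.

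Section 11 describes one further visit, Post-test II, nominally six weeks after treatment. It can fall later, because a rule covers that case: "if a child is being evaluated more than 6 weeks post treatment, don't administer probes". Part of its stated goal is to "administer perturbation tasks (NYU/MSU only) and accompanying perception tasks (all sites"). The task list has the /r/ probes, head-had identification and discrimination, and the reflexive and adaptive perturbation tasks at NYU/MSU. It has no safety check. The section names three checklists for the visit: all tasks, no perturbation, and no probes.

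**The concern.** Both safety questions look backwards from the day they are asked. A question put at Post-test I cannot cover anything after Post-test I. Two things come later: an interval of six weeks or more, and a visit with tasks listed at no earlier visit.

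At stake is the completeness of harm reporting in children aged 9 to 15. From the data scheduled in this document, the sponsor could not say from solicited reports whether the perturbation tasks were tolerated. Nor could it say whether an effect reported at Post-test I had resolved or persisted, or whether a new one had appeared. A summary of side effects over the study would in practice stop at the end of treatment. The plan does return to the children at Post-test II to see how their speech has changed since treatment, so the opportunity to ask already exists.

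**Working it through.** The plan states no figure on this point to reproduce. The check sets the visit schedule beside the safety schedule and then counts.

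**Inputs**
- Phase 0: 1 session (section 5).
- Phase I: 3 sessions (section 7).
- Phase II: 16 sessions (section 9).
- Safety checks: start of Generalization Session 7 (section 8) and Post-test I (section 10).
- Post-test II: six weeks after treatment or later (section 11).
- Target enrolment: 55 at each of MSU and Syracuse, 110 in total (opening summary).

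**Step 1: treatment sessions covered.** Counting the Phase 0 instruction session, there are 1 + 3 + 16 = 20 sessions.
- Before the Session 7 check: 1 + 3 + 6 = 10.
- Between the two checks: 16 − 6 = 10.
- After the Post-test I check: 20 − 10 − 10 = 0.

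For a child who reaches Post-test I, all 20 sessions fall inside the recall period of the second check.

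**Step 2: what is not covered.**

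| After the last scheduled safety question | Who |
|---|---|
| Interval from Post-test I to Post-test II, nominally 6 weeks, sometimes longer | All children still in the study |
| Head-had identification and discrimination | All sites |
| Reflexive and adaptive perturbation tasks | NYU/MSU only |
| /r/ probes, if the visit is not late | All sites |

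The probes were also given at earlier visits. The head-had tasks appear for the first time here, though identification and discrimination tasks with another word pair (rake-wake) were used before. The perturbation tasks have no earlier counterpart in the listed visits.

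**Step 3: number of children.** The enrolment sites are MSU and Syracuse, and the perturbation tasks are not given at Syracuse. The upper bound is therefore the MSU target: 55 of 110, or 55/110 = 50%. Dropout, or a missed Post-test II, lowers it.

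**Step 4: search for a later check.** No other section of the combined document schedules a safety question after Post-test I. The analysis plan contains no safety analysis, so nothing there implies a later collection point. Section 8 calls its procedure the Protocol for Safety Check, while section 10 refers to a Safety Monitoring Protocol. Neither is supplied, nor are the three Post-test II checklists.

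**The case against.** The strongest case for the present plan has four parts.

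**The period that matters most is covered.** All treatment sessions precede the Post-test I check. Asking then, before the site-specific tasks, also keeps treatment-period answers free of any effect of the perturbation tasks. This stands, and it is a good reason to leave the Post-test I check where it is.

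**A later question may exist elsewhere.** The cited safety protocol or the Post-test II checklists could contain one, and nothing bars spontaneous reports. This also stands. A reader might infer that late effects are never asked about, but the documents support only that no question is scheduled in this document. Against that, section 10 also cites a checklist and still writes its safety check out in full, so the silence of section 11 is unlikely to be mere delegation.

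**The label is not wrong.** A reader might take the word final to be contradicted by a later visit. It is not: section 8 schedules a midterm administration and section 10 the last of the two. The label makes no claim to follow every study procedure.

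**The uncovered share is easily overstated.** A reader might compute 1 + 8 + 6 = 15 weeks from the start of Acquisition and call 6/15 = 40% of the study unmonitored. That counts weeks in which no treatment is scheduled, leaves the evaluation sessions, Phase 0 and gaps between phases out of the denominator, and says nothing about exposure. It should not be used.

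It is also fair to say that the documents describe no risk from the perturbation tasks and no mechanism for late effects of speech practice. They give no figures from which the size of the risk could be judged, in either direction.

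**Conclusion.** The point holds in a limited form. As scheduled in this document, solicited side-effect questions stop at Post-test I. The interval to Post-test II and that visit's procedures are not covered, including the perturbation tasks for up to 55 of the 110 target children. The figure of 55 assumes that the MSU target is met and that every MSU child attends Post-test II and does the tasks.

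No endpoint, estimate or error rate is affected, and no known hazard is claimed. The conclusion rests on the unsupplied safety protocol and checklists holding no later question. If they do hold one, what remains is to say so in section 11. This is an inexpensive improvement in harm ascertainment, not a defect in the trial's main comparison.

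**What to change.** 1. Reconcile sections 8, 10 and 11 with the cited safety protocol, and state whether the two names refer to one document. If a later check already exists, cite it in section 11.
2. If none exists, keep the Post-test I check unchanged in timing, described as the end-of-treatment check.
3. Add the same two questions to all three Post-test II checklists, asked twice. On arrival, word them to cover the time since the child's last safety check, and follow up any effect reported earlier. After the last task, ask briefly again about that day's procedures. Both are needed: at MSU, a single question after the tasks would mix late effects of treatment with effects of the perturbation tasks, and tabulating by visit could not separate them.
4. Report the Post-test II answers separately from treatment-period reports and by site, because the perturbation tasks are not given at Syracuse.

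The cost is a short protocol edit, three checklist edits and a few minutes at an existing visit. No endpoint, treatment or visit changes. Children who miss Post-test II will lack the check, so the number asked should be given with the results.
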